The trial will be conducted in accordance with International Conference on Harmonisation Good Clinical Practice (ICH GCP), applicable United States (US) Code of Federal Regulations (CFR), and the National Institute of Mental Health Terms and Conditions of Award. The Principal Investigator will assure that no deviation from, or changes to the protocol will take place without prior agreement from the Investigational New Drug (IND) or Investigational Device Exemption (IDE) sponsor, funding agency and documented approval from the Institutional Review Board (IRB), except where necessary to eliminate an immediate hazard(s) to the trial participants. All personnel involved in the conduct of this study have completed Human Subjects Protection and ICH GCP Training.

The protocol, informed consent form(s), recruitment materials, and all participant materials will be submitted to the IRB for review and approval. Approval of both the protocol and the consent form must be obtained before any participant is enrolled. Any amendment to the protocol will require review and approval by the IRB before the changes are implemented to the study. All changes to the consent form will be IRB approved; a determination will be made regarding whether a new consent needs to be obtained from participants who provided consent, using a previously approved consent form.]

1 PROTOCOL SUMMARY

[figure not shown]
1.1 SYNOPSIS

| | |
|---------------------------|--|
| Title: | Automated Medication Platform with Video Observation and Facial Recognition to Improve Adherence to Antiretroviral Therapy in Patients with HIV/AIDS |
| Study Description: | This is an unblinded study of the HiDO automated medication adherence platform in patients ages 18 to 55 who are currently taking ART. From this population, 24 participants will be recruited to use the HiDO medication adherence platform for a 90-day intervention period. Medication adherence and device usability will be measured by various means. It is hypothesized that: a) use of HiDO will result in ≥95% medication adherence over 90 days; b) usability scores for the HiDO platform (as measured by Time on Task values and error rates) will be equal to or better than published benchmark rates for similar platforms; c) System Usability Scale (SUS) value will be >68; d) greater than 80% of participants will indicate that they are Likely or Strongly Likely to recommend the HiDO device to a friend or colleague. |
| Objectives: | 
Primary Objective: Determine the effect of automated medication adherence platform (HiDO) on medication compliance.
 
Secondary Objective: Determine usability of automated medication adherence platform (HiDO), as indicated by user ease of adoption (Time on Task, error rates), standardized user experience metric (SUS), and user endorsement (Net Promoter Score).
 |

| | |
|--|---|
| Endpoints: | Primary Endpoint: Medication adherence as assessed by remote observation through the HiDO device at 90 days. Secondary Endpoints: Time on Task for initial registration, “first click” testing, facial recognition setup, medication administration, number and type of critical and non-critical errors and error-free rate, System Usability Scale (SUS), Net Promoter Score. |
| Study Population: | Sample of 24 participants from U.S. population of individuals ages 18 and older who are currently taking antiretroviral therapy (ART). |
| Phase: | 1 |
| Description of Sites/Facilities Enrolling Participants: | HiDO Technologies [name] |
| Description of Study Intervention: | HiDO is an automated Artificial Intelligence driven direct observation medication adherence platform. The platform is a 510K exempt Class I medical device (890.5050) that integrates medication dispensing, dose administration time, pill count and front facing video cameras to validate the right medications, at the right time to the right patient. The device dispenses up to 7 different types of medications simultaneously. The camera logs every dose using facial recognition and provides real time consumption logs. Investigators have access to video observation logs, patient dose time, adherence trends, and study level adherence measures. For this study, the HiDO medication adherence platform will be delivered to the residence of each participant by the researcher, who will provide instructions for performing device setup that includes linking the HiDO device to the participant’s smartphone and filling the device with ART. The participant receives a smartphone alert when it is time to take a medication, and then pushes the button on the device to receive the correct medicine at the given time. If the patient does not respond, additional reminders are sent via phone and SMS. Medication adherence will be measured over 90 days using the HiDO device. Additionally, participants will participate in a semi-structured interview following the 90-day period to assess system usability. |
| Study Duration: | 12 months |
| Participant Duration: | 104 days |

1.2 SCHEMA

Figure 1. Study Schema for, “Automated Medication Platform with Video Observation and Facial Recognition to Improve Adherence to Antiretroviral Therapy in Patients with HIV/AIDS

1.3 SCHEDULE OF ACTIVITIES (SOA)

| Procedures | Screening / baseline measurement Day -14 to -1 | Week 1, Day 1 (Completion of platform setup) | Week 2, Day 14 +/-1 day | Week 4, Day 28 +/-1 day | Week 6, Day 42 +/-1 day | Week 8, Day 56 +/-1 day | Week 10, Day 70 +/-1 day | Week 12, Day 84 +/-1 day | Week 13, Day 90 +/-1 day | Week 14, Day 97 +/-7 days |
|--|---|---|----------------------------|----------------------------|----------------------------|----------------------------|-----------------------------|-----------------------------|-----------------------------|------------------------------|
| Informed consent | X | | | | | | | | | |
| Demographics | X | | | | | | | | | |
| Medication adherence self-report | X | | | | | | | | | |
| Delivery of HiDO platform | X | | | | | | | | | |
| Assisted platform setup | X | | | | | | | | | |
| Time on Task | X | X | X | | | | | | X | |
| Error rate | X | X | X | | | | | | X | |
| Automated medication adherence | | X-----X | | | | | | | | |
| Device log audit | | | X | | X | | X | | | X |
| Usability assessment (semi-structured interview) | | | | | | | | | | X |
| Adverse event review and evaluation | | X-----X | | | | | | | | |
| Complete Case Report Forms (CRFs) | X | | | | | | | | | |

2 INTRODUCTION

2.1 BACKGROUND INFORMATION

HIV drug treatment saves lives. Antiretroviral therapy (ART) has directly and irrefutably reduced the death rate of people with HIV/AIDS. Because of public health measures including the administration of ART, AIDS-related deaths declined by 38% from 2000 to 2017—saving more than 11 million lives worldwide.¹ A high degree of adherence to ART is an essential part of this success. People living with HIV (PLWH) who strictly follow their ART regimens can control the disease. For example, 102 patients with acute or early HIV-1 infection were prospectively followed; 97% of those who strictly followed ART had undetectable viral levels at a median of 11 weeks and 92% had continued viral suppression at 18 months.² When HIV is suppressed in this way, the risk-of developing an AIDS-defining condition is greatly reduced.³ In fact, the immune system can even reconstitute itself.⁴ Moreover, patients who achieve viral suppression do not transmit HIV to others.⁵⁻⁷ Likewise, people at high risk who consistently take daily pre-exposure prophylaxis (PrEP) can substantially reduce their risk of acquiring HIV infection.⁷ The same protective effect has been observed for post-exposure prophylaxis (PEP); however, the key to the success of ART, PrEP and PEP is strict adherence.

Nonadherence in clinical trials has profound economic and societal costs. Medication adherence is critically important during clinical trials. Investigators insist on (or assume) adherence rates of $\geq 95\%$, however, substantial evidence exists that actual adherence in trials is far less than that.^{8,9} Gossec et al. performed a meta-analysis of 192 publications of RCTs in six chronic conditions and observes a median compliance of 93% through pill count adherence measures.¹⁰ However, when bodily fluid measurements

were used to assess adherence in this same population, the values were substantially lower, 54% to 68%.⁹ This means that pill count is an inaccurate measure of adherence and true medication adherence rates are below 70%.⁹ High levels of medication adherence are perhaps no more important than they are in HIV clinical trials. Considering that patients with adherence rates of <95% are 3.5 times as likely to have treatment failure as defined as HIV-1 RNA >50 copies/ml than those with 95% adherence or greater.¹¹ While recent work using real world data has suggested that HIV viral suppression may be possible with adherence rates as low as 80%, this appears to be ART regimen-dependent.¹² Since we know that viral suppression is now possible with ART and interrupting transmission is possible with PrEP and PEP, the FDA will almost assuredly require viral suppression as an endpoint in anti-HIV medication trials. Compliance of less than 68% will cause IMPs to fail. If participants in a placebo-controlled trial are taking less than 70% of their study medication doses, the effect in active arm will be underestimated. Poor actual adherence during clinical trials skews data, confounds statistical analyses, increases participant discontinuation rates, lengthens recruitment periods and extends the total duration of clinical trials.¹³ Non-adherence is directly responsible for longer and more costly clinical trials.¹³ These costs are estimated to be in excess of \$1.5 billion capitalized over the time required to develop a single new investigational medicinal product (IMP).⁹ This not only costs clinical trial sponsors substantial sums of money, but it slows the development of new therapies and decreases the pool of eligible study participants in future trials (e.g. most trials exclude potential participants who recently participated in a clinical trial). Timeline expansion translates to \$600,000 per day in lost revenue opportunity for products with focused indications and up to \$8 Million per day for broadly used medications.¹³

Efforts to improve adherence are only modestly successful. Multiple factors contribute to nonadherence.¹⁴ These factors include the complexity of taking medications, time burden on the patient, the patient's perception of benefits and risks. Several measures have been proposed and deployed to improve adherence. These include behavioral skills training, medication adherence training, phone reminders, text reminders, smart pill caps, and various combinations thereof. Karters and colleagues systematically reviewed 85 medication adherence trials comprising 16,271 participants and after conducting a network meta-analysis concluded, "Several interventions can improve adherence and viral suppression; generally, their estimated effects were modest and waned over time."¹⁵ The usual methods for monitoring adherence in clinical trials are self-reported medication adherence, pharmacy refill data, Medication Event Monitoring Systems, and therapeutic drug monitoring. Each of these methods has its strengths and weaknesses; but none can be considered a gold standard because of their inherent limitations. Direct observation could be the gold standard, but it is prohibitively expensive and impractical.

Directly observed therapy could be a solution. Directly observed therapy is a means of encouraging strict medication adherence in which a health-care worker or other competent individual physically watches a patient consume their medication. Given the importance of strict medication adherence in HIV/AIDS, there have been efforts to institute directly observed therapy adherence measures.^{16,17} A systematic review and meta-analysis showed that directly-observed therapy of ART "had a significant effect on virologic, immunologic, and adherence outcomes."¹⁸ In-person, directly observed therapy has its critics, however. They suggest it is coercive, dehumanizing, and hinders autonomy.¹⁹⁻²¹

2.2 RATIONALE

Directly observed therapy could be the gold standard for HIV, but the process must eliminate the burden of travel, the loss of autonomy and the high cost of direct observation. Poor medication adherence is an ongoing problem in clinical trials, especially in medications to treat HIV/AIDS. Even high potency, low genetic resistance ART regimens require adherence above 80% (and recommended adherence is greater than 95% regardless of agents). This means they fail to achieve viral suppression, are a source of drug-resistance strains of HIV, are more difficult to treat, can advance to AIDS, and acquire opportunistic infections and develop AIDS-related cancers. In clinical trials, poor adherence skews data, making the active arm seem less potent than control. Drug development programs may be scuttled due to poor and unrealized poor adherence.

The purpose of the current study is to test the effectiveness of HiDO, an automated medication adherence platform, in both improving medication adherence among HIV/AIDS patients and providing a better user experience compared to existing medication adherence devices.

Hypothesis 1: Use of the HiDO automated medication adherence platform will result in ≥95% medication adherence over 90 days.

Hypothesis 2: Usability scores for the HiDO platform (as measured by Time on Task for initial registration, “first click” testing, facial recognition setup, and medication administration, number and type of critical and non-critical errors, and error-free rate) will be equal to or better than published benchmark rates for similar platforms.

Hypothesis 3: The System Usability Scale (SUS) value for the HiDO platform will be equal to or better than published benchmark rates for similar platforms (>68).

Hypothesis 4: Greater than 80% of participants will indicate that they are Likely or Strongly Likely to recommend the HiDO device to a friend or colleague.

HiDO is an automated AI (Artificial Intelligence)-driven, direct observation medication adherence platform. The platform is a 510K exempt Class I medical device that integrates medication dispensing, dose administration time, pill count and a front-facing video and infrared cameras to validate the right medications, the right time go to the right patient. The camera logs every dose using facial recognition and provides real-time consumption logs. Investigators have access to video observation logs, patient dose time, adherence trends, and study-level adherence through the platform's dashboard. Study participant can set up the device in minutes using their smartphone. Data is stored securely in the cloud and accessible in real-time. The technology has been awarded a provisional patent.

Medications may be filled by a pharmacist or clinical trial site. The device is not locked, which allows patients to retrieve or refill medications manually if needed, but notifies the researcher whenever the closing mechanism on the back of the unit is opened. A cap is selected that indicates the pill size and type, which is then placed on the pill bottle. The 40-dram (5 oz.) bin for each medication is inserted into the HiDO unit; up to 7 different medications can be housed at one time in separate bins. The HiDO unit senses the medication(s) and dispenses the medication(s) at the specified time and dosage level. Patients are alerted by the desktop HiDO unit and via smartphone when it is time to take their medication. Facial recognition software detects the patient through front-facing video cameras and identifies that it is, indeed, the person who is supposed to take the medication. The camera records and confirms that the patient consumes the medication, recording the exact time and medication(s) taken. The patient, caregivers, health care team (and clinic trial investigators) can track medication adherence in real time using a dashboard. The HiDO device enables remote monitoring and can also collect patient-reported outcomes, adverse events, disease symptoms, treatment satisfaction, and other data.

HiDO is the first device of its kind to integrate medication reminders, patient reported outcomes, drug dispensing, and remote/recorded observed therapy in a single platform (see Figure 2). The device collects real-time data for medication adherence, dose administration time, 14-day adherence trend analysis and video recording of medication consumption. These capabilities help satisfy the new FDA remote-monitoring guidance issued August 2020. Both pharmaceutical and clinical trial organizations have expressed interest in leveraging the HiDO device across the HIV and other drug development pipelines. While clinical trialists do use body fluid sampling to assess adherence, the advent of COVID-19 has dramatically reduced in-person clinical trial visits. Sponsors are aggressively pursuing ways to meet FDA requirements with fewer in-person visits.

Figure 2. Comparison of HiDO with available medication adherence platforms.

| Product | Description | Pros | Cons |
|---------|---|---|--|
| HiDO | Automated video-observed therapy and medication dispenser | 
 Sorts and dispenses pills Observes and records therapy Facial recognition biometrics Tracks drug administration Medication reminders Holds up to 7 drugs x 40 doses Can be used with standard pill bottle | 
 Some patients may not like video recording |
| Proteus | Ingestible sensor | 
 Completely assures drug is swallowed | 
 Patients don't like swallowing a device Patients must track their own medications and regimen No integrated reminders FDA approval required for each molecule (very costly) |
| AiCure | Video-observed therapy via smartphone | 
 Observes and records therapy Facial recognition biometrics | 
 Patients must be able to hold the phone properly to engage the device Cumbersome and tedious Some patients may not like video recording |
| Livi | Medication dispenser | 
 Sorts and dispenses pills Tracks drug administration | 
 Does not observe therapy Uncontrolled ejection of pills or pills get stuck Large, bulky unit Does not detect pills Not a "smart" unit High user burden |
| Pillo | Medication dispenser with biometrics | 
 Facial recognition Medication reminders Anthropomorphized "face" on dispenser | 
 Does not record drug administration or confirm drug consumption Only holds 28 doses Each pill needs to be loaded individually |
| Pillsy | Smart pill cap, MEMS | 
 Medication reminders on app and phone Can be used with standard pill bottle | 
 Patients can open the cap to stop alert but not take the drug Does not record drug administration or confirm drug consumption |
| URSure | Urine ART testing | 
 Confirms drug was taken | 
 Creates a negative user experience; people are drug tested like criminals Limited scope of accuracy; valid only 4-7 days; requires frequent testing |

Demonstrating the feasibility of the technology proposed in this application is a critical step in device development. The data collected during this study will allow HiDO to refine and finalize the platform. It will also demonstrate preliminary impact, which will be important for determining whether the technology should be further developed and will likely be one of the factors that attracts financial

investors. Additional funding of a successful medication adherence device will allow expansion and commercialization of this platform, which can lower the costs of and disruptions to clinical trials, improve medication adherence in vulnerable patient populations, and ultimately change the trajectory of HIV/AIDS morbidity and mortality on a population level.

2.3 RISK/BENEFIT ASSESSMENT

2.3.1 KNOWN POTENTIAL RISKS

A potential risk to participants is breach of confidentiality, which exists both as an immediate and long-term risk. There is also an immediate risk that the platform hardware or software may malfunction in some way, which may affect data capture, data transmission, or medication dispensing. These errors may affect the reliability of the device in providing timely dosage reminders, accurate remote monitoring, and accurate dispensing of medication.

2.3.2 KNOWN POTENTIAL BENEFITS

Participants may directly benefit from better and more consistent medication adherence resulting from use of the HiDO platform, which would increase the chance of achieving and maintaining viral suppression. Participants, as well as the population at large, may experience indirect long-term benefit from the development of automated medication adherence platforms that improve treatment outcomes and lower the cost of new drug development (as described previously in Section 2.2, Rationale).

2.3.3 ASSESSMENT OF POTENTIAL RISKS AND BENEFITS

The risk of breach of confidentiality risk is mitigated through use of stringent data security procedures. Data collected through the HiDO device is stored on Amazon Web Services (AWS), a HIPAA-compliant cloud computing platform. Other electronic data not stored on the AWS cloud platform are stored locally on encrypted and password-protected computers accessible only to the research staff. Any paper records generated are stored in locked cabinets accessible only to the researcher staff. Data accessed from clinical records are de-identified prior to being recorded into the research database.

Regarding the risk of device malfunction, these risks are unavoidable to some degree, given that the purpose of the study is to assess device functioning. To mitigate the risk to participants posed by platform malfunctions, participants are advised of these risks and reminded to adhere to their prescribed ART treatment protocol in the event that the device malfunctions, both during the consent process and with written instructions included in HiDO device packaging (see Appendix A: HiDO Product Brochure). Additionally, participants are able to manually access medications loaded into the device, should the device fail to dispense them automatically.

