3 OBJECTIVES AND ENDPOINTS

| OBJECTIVES | ENDPOINTS | JUSTIFICATION FOR ENDPOINTS |
|---|--|--|
| Primary | | |
| Determine the effect of automated medication adherence platform (HiDO) on medication compliance. | Mean adherence rate to ART in all patients across 90 days (quantified as (n. of doses provided — n. of doses taken) / n. of doses provided x 100) | Adherence data are automatically and continuously recorded by HiDO device, and directly confirmable through manual audit of video recordings. |
| Secondary | | |
| Determine usability of automated medication adherence platform (HiDO), as indicated by user ease of adoption (Time on Task, error rates), standardized user experience metric (SUS), and user endorsement (Net Promoter Score). | 
Measured at Week 2:
 
 • Time on Task for initial registration • Time on Task for “first click” testing • Time on Task for facial recognition setup • Time on Task for medication administration • Number and type of critical and non-critical errors • Error-free rate 
Measured after 90 days use of platform:
 
 • Score on System Usability Scale (SUS) • Net Promoter Score | 
Time on Task and error rates may be compared to published benchmarks for similar platforms.
 
According to usability.gov published by the U.S. Department of Health & Human Services, the SUS is regarded as a reliable tool to assess usability and has become the industry standard.²⁴ Results from the SUS have been published in over 1,300 publications.²⁴ It can be used on small sample sizes with reliable results and can effectively discriminate between usable and unusable systems.
 
The Net Promoter Score is based on the response to the question, “How likely is it that you would recommend our device to a friend or colleague?” on a 5-point Likert scale.
 |

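### The primary endpoint has no rule for ART doses taken by hand during a device malfunction, and the choice of rule can decide whether 95% is reached

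*Combined protocol and SAP*

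**What the plan says.** The Synopsis (Section 1.1) gives the primary endpoint as "Medication adherence as assessed by remote observation through the HiDO device at 90 days". Section 3 words it as "Mean adherence rate to ART in all patients across 90 days", with the formula "n. of doses provided — n. of doses taken) / n. of doses provided x 100". As printed, that formula gives the percentage of doses not taken; I assume doses taken over doses provided is meant. Neither term is defined.

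Section 2.3.1 accepts that hardware or software may malfunction, "which may affect data capture, data transmission, or medication dispensing". Section 2.3.3 says participants are "reminded to adhere to their prescribed ART treatment protocol in the event that the device malfunctions", and that "participants are able to manually access medications loaded into the device, should the device fail to dispense them automatically". Section 2.2 describes an unlocked unit, "which allows patients to retrieve or refill medications manually if needed, but notifies the researcher whenever the closing mechanism" at the back is opened. Section 6.1.1 says filming begins only once facial recognition has unlocked the device and the dispensing has been verified.

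Section 9.1 sets the null hypothesis at below 94% and the alternative at 95% or more. Section 9.4.2 settles the matter with descriptive statistics alone. Sections 3, 9.3 and 9.4 do not say how a dose taken outside the device enters the numerator or the denominator.

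**The concern.** The protocol expects malfunctions, expects participants to go on taking ART during them, and gives them a manual route to the pills. The measuring instrument for the primary endpoint is the same device that has then failed. A dose removed from the back of the unit and swallowed produces no video, so the plan needs a rule for it.

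Two rules are open under the wording. If doses provided are the scheduled doses, the swallowed dose counts as non-adherence. If they are the doses the device dispensed, the dose disappears from numerator and denominator, and the failure disappears with it. The second sits badly with Section 2.3.3, which describes the study as an assessment of how the device functions.

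The hypotheses are one percentage point apart and the point estimate carries the conclusion, so the counting rule can settle the primary result. Section 8.2 uses the same logs to detect a device that lowers adherence. That signal could be falsely raised under one rule and masked under the other.

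**Working it through.** The plan gives no malfunction rate and no count of off-device doses, so there is no figure of its own to reproduce. The check is how few such doses matter.

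**Inputs from the protocol:** 90 days (Section 3); 94% and 95% thresholds (Section 9.1).

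**Assumptions:** one dose a day, since dosing frequency is not stated; T = adherence on days the device works; m = average number of malfunction doses per participant. The endpoint is a mean, so with equal follow-up only the average m matters.

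**Size of the threshold gap.** One dose is 1/90 = 1.1 points. The 94% to 95% gap is 0.01 × 90 = 0.9 dose. A 95% result allows 0.05 × 90 = 4.5 unobserved doses.

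**Formulas**
- Actual intake, malfunction doses all taken by hand: (T(90 − m) + m)/90
- Scored as missed: T(90 − m)/90
- Dropped from the denominator: T

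| T | m | Actual, if taken by hand | Scored as missed | Dropped |
|---|---|---|---|---|
| 97% | 1 | 97.0% | 95.9% | 97.0% |
| 97% | 2 | 97.1% | 94.8% | 97.0% |
| 97% | 3 | 97.1% | 93.8% | 97.0% |
| 98% | 3 | 98.1% | 94.7% | 98.0% |
| 98% | 5 | 98.1% | 92.6% | 98.0% |
| 100% | 5 | 100% | 94.4% | 100% |

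**Break-even.** Scored as missed, the mean falls below 95% when m > 90(1 − 0.95/T):
- T = 97%: 90(1 − 0.95/0.97) = 1.9 doses
- T = 98%: 90(1 − 0.95/0.98) = 2.8 doses
- T = 100%: 90(1 − 0.95) = 4.5 doses

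At T = 97% it enters the null region, below 94%, when m > 90(1 − 0.94/0.97) = 2.8 doses. The 94.8% at m = 2 falls between the two hypotheses, where neither applies.

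**The opposite error.** If the malfunction doses were not taken, with T = 98% and m = 5, actual adherence is 0.98 × 85/90 = 92.6%. The dropped rule still reports 98.0%.

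At two doses a day the percentages are the same for the same number of malfunction days.

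**The case against.** The strongest reply is that the protocol has other sources. The logs are audited by hand (Sections 4.1 and 6.4), back-openings are notified, anomalies are flagged for resolution (Section 10.1.8), and adherence is self-reported before and after the study. A third treatment, crediting a dose after adjudication, is therefore conceivable. It is not specified, though. An audit cannot recover a dose that was never filmed, an opening shows access and not ingestion, and self-report is outside the primary endpoint. Section 4.2 deals only with participants who withdraw completely.

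It is also fair to say that this is a descriptive pilot and that the malfunction numbers are mine. Both stand. They limit how firmly the size can be stated but do not supply the missing rule.

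A reader might infer more than the documents support:
- **That participants are told to dose by hand.** Section 2.3.3 reminds them to adhere and says manual access is possible.
- **That dropping doses always overstates adherence.** When the doses were taken, the table shows the dropped figure equal to or slightly below actual intake. It overstates only when they were not taken.
- **That device failures would go wholly unseen.** Error counts and the error-free rate are secondary endpoints, though collected only at set time points.
- **That every malfunction yields an unfilmed dose.** Section 2.3.1 also lists transmission faults, and the documents do not say whether those recordings are lost.
- **That the unit must be opened at least twice for refills.** Figure 2 in Section 2.2 says "Holds up to 7 drugs x 40 doses", and 90/40 = 2.25 fills, but this needs once-daily dosing and one bin per drug. The documents state neither, and the device's pill count might help separate refills from removals.

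**Conclusion.** The gap is real and should be closed before analysis. Doses taken outside the device are foreseen by the protocol, are not filmed, and have no place in the primary endpoint as defined. Under the scheduled reading adherence is understated; under the dispensed reading device failure is hidden, and adherence is overstated whenever the doses were not taken.

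The rule can decide the result. With one dose a day and 97% adherence on working days, about 1.9 hand-taken doses per participant separate a mean below 95% from one of 97%. At 98% and 100% the figures are 2.8 and 4.5. These are illustrations under assumed inputs. The documents do not show how often malfunctions will occur, so they do not support a forecast that the endpoint will be missed or met because of them.

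**What to change.** 1. Set the denominator to scheduled (prescribed) doses, and correct the Section 3 formula so that it gives the share taken.
2. Keep video-confirmed over scheduled doses as the primary measure, described as a conservative measure of device-confirmed adherence. It understates intake when hand-taken doses occur, and the text should say so.
3. From the existing dose logs, log audits and back-opening notifications, flag each scheduled dose that has no video and coincides with a recorded malfunction or a back-opening.
4. Report one sensitivity analysis that counts every flagged dose as taken. The primary result is then the lower bound and this the upper.
5. Report the share of scheduled doses flagged.

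The cost is a definition, one derived flag and two extra lines in the results. No participant confirmation during the 90 days is needed. That would be new data collection: self-report is only pre- and post-study, and the footnote in Section 6.1.1 says the device's survey feature is not used. It could also act as a prompt of the kind Section 5.5 rules out. No instruction to participants changes.

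There are two downsides. The headline may be less favourable, because device failures count against it. Openings for refills cannot always be told apart from manual doses, so the upper bound is generous. The documents describe no continuous outage log, so a malfunction that leaves no record would still be scored as missed; the report should state this.
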